2.0 Synopsis

Short Title	The PROMIZING Study
Study Title	Proportional Assist Ventilation for Minimizing the Duration of Mechanical Ventilation: The PROMIZING Study
Trial Design	Multi-centre, open-label RCT
Study Participants	Adult patients receiving MV for acute respiratory failure who are ventilated in A/C mode, ready to be maintained with partial ventilatory support (PSV) but not yet ready for extubation (not yet ready for an SBT or failed an SBT)
Investigational Product/Device	Proportional Assist Ventilation with load-adjustable gain factors (PAV+), PB 840 or 980 ventilator, (Covidien LP, a Medtronic company)
Investigational Intervention	Study participants will be randomized to one of two arms. The control is the standard of care PSV ventilation strategy, designed to adjust the level of support according to usual clinical parameters. The intervention is a PAV+ ventilation strategy, designed to adjust the level of support (gain) to target a predefined range of respiratory muscle pressure.
Planned Sample Size	558(279 each PAV+ and PSV) is the minimum planned sample size.
Treatment/Follow up Duration	The expected duration of patient participation is approximately 21-90 days, including screening and follow-up procedures and depends on the length of time the patient remains on MV in the ICU. Patients will be followed with daily data collection until they remain free of invasive mechanical ventilation for 7 days. Date of live ICU discharge or ICU death, live hospital discharge or hospital death will also be recorded for each randomized patient. Vital status will be determined at 14, 21, 28 and 90 days post randomization.
Planned Study Period	Planned enrolment period is Sept 2016- Sept 2021. The study will continue to enrol patients until we have complete data on participants containing required number of events for analysis. Patient follow up is targeted to end December 2021.
Primary Outcome	Time from randomization to successful liberation from invasive mechanical ventilation


Secondary Outcomes
	
 (i) Ventilator-free days at day 14, 21,28 days post randomization, (ii) Time from randomization to live ICU discharge (up to day 90), (iii) Time from randomization to live hospital discharge (up to day 90), (iv) Mortality, measured as ICU mortality; hospital mortality; 14, 21, 28, and 90 day mortality (v) Weaning Progress, measured as time from randomization to: first SBT; first successful SBT; first extubation. (vi) Weaning Difficulties, measured as the number of patients failing first SBT or first extubation attempt and requiring up to 7 days to extubate (difficult weaning group/ group 2); failing first SBT or first extubation attempt and requiring more than 7 days to extubate (prolonged weaning group/ group 3), (vii) Weaning Complications, measured as the number of patients: requiring non-invasive ventilation post-extubation; ventilated more than 7 days post randomization, ventilated more than 21 days from time of intubation (prolonged MV group); receiving tracheostomy post randomization, requiring reintubation (up to 7d after planned extubation) (viii) Tolerance of modes, measured as number of patients ever requiring A/C mode post randomization; number of patient-days requiring A/C mode post randomization, (ix) Cumulative dose of narcotics (converted to morphine equivalents); benzodiazepines (converted to midazolam equivalents); propofol, and dexmedetomidine (x) Number of patients and number of patient-days receiving any antipsychotic medication (xi) Sensitivity analyses of primary and secondary outcomes defining “successful extubation” as “48 hours without reintubation” (xii) Sensitivity analyses of primary and secondary outcomes assigning a value of 0 ventilator-free days to any participant who dies at any time during the study period

A priori Subgroup Analyses
	
 (i) duration of MV prior to randomization greater than 5 days (ii) failed SBT vs. failed CPAP 0 trial vs. failed weaning criteria prior to randomization (iii) failed extubation prior to randomization (iv) mild, moderate, severe frailty

3.0 Abbreviations

A/C	Assist/Control
AE	Adverse Event
AHRC	Applied Health Research Centre
CC	Coordinating Centre
CMV	Controlled Mechanical Ventilation
CPAP	Continuous Positive Airway Pressure
CRF	Case Report Form
DSMB	Data Safety Monitoring Board
EC	Executive Committee
eCRF	Electronic Case Report Form
ICU	Intensive Care Unit
MV	Mechanical Ventilation
PAV+	Proportional Assist Ventilation with load-adjustable gain factors
PEEP	Positive End-Expiratory Pressure
PSV	Pressure Support Ventilation
RCT	Randomized Controlled Trial
REB	Research Ethics Board
SAE	Serious Adverse Event
SBT	Spontaneous Breathing Trial
SDM	Substitute Decision Maker
VFD	Ventilator-Free Day

4.0 Introduction

4.1 Study Conduct

This study will be conducted in compliance with the protocol approved by Research Ethics Boards (REBs) and according to ICH Good Clinical Practice standards.

The study has been registered on www.clinicaltrials.gov prior to participant enrolment (NCT02447692).

4.2 Background

4.2.1 Study Rationale

Patients with acute respiratory failure require invasive mechanical ventilation (MV) to support their work of breathing and provide adequate gas exchange until they recover from their acute illness. Upon initiation of invasive MV, the goal is to wean and liberate patients from MV as soon as they can manage breathing unsupported. However, MV itself may induce respiratory muscle weakness,[1-3] patient-ventilator dyssynchrony,[4;5] and necessitate the administration of sedative drugs, all of which have been associated with a prolonged duration of dependence on MV. Prolonged dependence on MV contributes to increased patient complication rates, intensive care unit (ICU) length of stay, and is associated with increased mortality.[6;7] Therefore, a major goal in caring for patients with acute respiratory failure is to reduce the duration of weaning and increase the number of patients successfully liberated from MV[8]. Avoidance of respiratory muscle atrophy, patient-ventilator dyssynchrony, and heavy sedation are potential means of achieving this goal, although this has not been definitively proven. Theoretically, respiratory muscle atrophy and patient-ventilator dyssynchrony should be minimized if the level of ventilator assistance is adjusted to target normal or reasonable levels of respiratory effort.[5;9;10]

Proportional assist ventilation with load-adjustable gain factors (PAV+) is a mode of mechanical ventilation which delivers assistance to breathe in proportion to the patient's effort. The proportional assistance, called the gain, can be adjusted by the clinician to maintain the patient's respiratory effort or workload within a reasonable range. This is the only mode of ventilation which allows for measurement and targeting of a specific range of respiratory muscle activity by the patient. Pressure support ventilation (PSV) is a mode of ventilation which is considered the current standard of care for assisting breathing of patients during the recovery phase of acute respiratory failure. Several studies have shown short term advantages of PAV over PSV, including improved patient-ventilator synchronization, improved adaptability to changes in patient effort, and improved sleep quality.[5;11-14]

The objective of this multi-centre randomized controlled trial is to determine if, for patients with acute respiratory failure, ventilation with PAV+ will result in a shorter duration of time spent on mechanical ventilation than ventilation with PSV.

4.3 Description of Intervention

The intervention is proportional assist ventilation with load-adjustable gain factors: PAV+™, Puritan Bennett™ 840 or 980 ventilator (Covidien LP, a Medtronic company, Boulder, USA). Sites will confirm prior to participation that the correct device and settings are available.

This mode of ventilation (PAV+) and this device (Puritan Bennett™ 840 or 980 ventilator) are approved for use in all countries with participating centres:

Health Canada Information: First Issue Date: 19Sep2005, Device name: 840 VENTILATOR SYSTEM - PAV UPGRADE KIT, Device Identifiers are 4-078204-00 and 4-078206-00

Europe Information: Issue Date: 19Jan2005, Release/Change per ECO-R151570, Device name: 840 VENTILATOR SYSTEM, SOFTWARE OPTIONS AND 806 COMPRESSOR, 840 Ventilator CE Marked Software Options , Device Identifiers for PAV+ Option are 4-078195-00 (Spanish), 4-078196-00 (French), 4-078198-00 (Italian) and Device Identifiers for PAV+ Upgrade are 4-078205-00 (Spanish), 4-078206-00 (French) and 4-078208-00 (Italian).

Argentina Information: First Issue Date: 06June2011, Device name: SISTEMA DE VENTILACION 840-KIT DE ACTUALIZACION PAV, Device Identifier is 4-078205-00.

Proportional assist ventilation with load-adjustable gain factors (PAV+) is a unique ventilatory mode that delivers assistance in proportion to patient effort, thereby allowing for titration of the balance between respiratory muscle capacity and load, and ensuring that the respiratory muscles are utilized throughout the breath and not just for triggering the breath. In PAV+ mode, the ventilator measures the instantaneous flow and volume generated by the patient and calculates the instantaneous pressure needed to overcome the elastic and resistive pressures. This is achieved by performing automated and repeated measurements of respiratory system compliance and resistance. This automatic adjustment has been implemented recently, justifying the acronym PAV⁺. Assistance (or gain) from the ventilator, which is adjusted by the clinician, is expressed as a percentage of the total pressure needed to inflate the respiratory system. Because of its working principles, PAV+ is the only mode which enables estimation of the pressure generated by the respiratory muscles. This can be made at the bedside from the values of the gain and the driving inspiratory airway pressure.

Patients will be randomized to either the PAV+ Ventilation Strategy, using a Puritan Bennett 840™ ventilator equipped with PAV+™, (intervention arm) or the PSV Ventilation Strategy, using any ventilator equipped with PSV (control arm).

In the PAV+ strategy, the level of support (gain) will be adjusted to target a respiratory muscle pressure within normal range. In the PSV strategy, the level of support will be adjusted according to usual clinical parameters (See Appendix C and Appendix D respectively). In both arms, patients developing respiratory distress or clinical instability will be changed to A/C mode and reassessed within 24 hours for criteria to resume PAV+ or PSV according to treatment allocation.

4.4 Clinical Data to Date

4.4.1 Clinical Data

Several physiological studies have shown important potential advantages of PAV compared to PSV including improved synchronization adaptation to changes in ventilator demand and improved sleep quality during short term ventilation. A relatively large single centre RCT but limited to a 48 hour period showed that significantly more patients could be ventilated with PAV+ than with PSV (94.4% vs 71.0%, $p < 0.001$) [15] and a pilot single centre RCT by [name] showed a two day reduction in ICU length of stay with PAV+ compared to PSV (median[IQR] 7.3[5.2-11.4] days on PAV+ vs. 12.4[7.5-30.8] days on PSV, $p = 0.03$).[16]

4.4.2 Safety Data

In the study by [name], there were no adverse events (pneumothorax, arrhythmia or death) resulting from the study interventions ($n = 54$ patients) [16]. As a safety mechanism, studies of PAV+ have utilized “intolerance criteria” for switching to another mode of ventilation, typically utilizing assist-control as the default mode for

patients who meet pre-specified criteria for respiratory distress despite optimization of PAV+ or PSV. As such, there are no reported cases of patients experiencing an adverse event as a physiological consequence of excessive work of breathing or instability due to PAV+.

The studies of PAV+ have demonstrated that PAV+ is generally well tolerated in patients meeting enrolment criteria for these studies. In the study by [name], patients tolerated PAV+ an average of 18.1 ± 5.9 hours/day and tolerated PSV 18.8 ± 5.0 hours/day in the PSV group ($p=0.64$). Over the duration of the study, total time spent on PAV+ ranged from 18 to 565 hours, or 10 to 100% of the study period (mean $75.3 \pm 24.6\%$), and in the PSV group, time spent on PSV ranged from 19 to 743 hours, or 28 to 100% of the study period (mean $78.4 \pm 21.0\%$). [16] A study by Xirouchaki et al., which examined tolerance of PAV+ and PSV for 48 hours in critically ill patients, found successful tolerance in 89% and 78% of patients on these respective modes. [15] A pilot study by Carreaux et al. study found one of 53 patients to be intolerant to PAV+; median time spent on PAV+ was 3 days [IQR 1-5] for the remaining 98% of patients who tolerated PAV+ for some duration of the study period. [17]

4.4.3 Pilot Data for this study design

The design of this trial is based upon two pilot studies. The eligibility criteria, method of recruitment, staged enrolment process, randomization to two equivalent ventilation strategies, criteria to initiate and method of weaning were piloted by [name] and coworkers in the single centre pilot RCT ($n=54$). [16] The ventilation algorithm to adjust PAV+ gain to maintain respiratory muscle workload within the normal range was piloted by [name] and colleagues in a multi-centre study ($n=52$). [17] Most of the centres participating in The PROMIZING Study were involved in one of these two studies. Both studies demonstrated safety, feasibility, and compliance with study protocol.

5.0 Study Objectives

The primary objective of this study is to determine if, for patients with acute respiratory failure, ventilation with PAV+, instituted early in the recovery phase and set to maintain a workload of breathing within the normal range, will result in a shorter duration of time spent on mechanical ventilation than ventilation with PSV.

The secondary objective of the study is to determine if other clinically important outcome measures are better with PAV+ as compared to PSV.

6.0 Study Design

6.1 General Design

This clinical study is a multi-centre open-label, RCT.

6.2 Primary Study Endpoints

The primary outcome is time from randomization to successful liberation from invasive mechanical ventilation.

6.3 Secondary Study Endpoints

The secondary outcome measures are:

- (i) Ventilator-free days at day 14, 21 and 28 post randomization,
- (ii) Time from randomization to live ICU discharge (up to day 90),
- (iii) Time from randomization to live hospital discharge (up to day 90),
- (iv) Mortality, measured as ICU mortality; hospital mortality; 14, 21, 28, and 90 day mortality
- (v) Weaning Progress, measured as time from randomization to: first SBT; first successful SBT; first extubation.

- (vi) Weaning Difficulties, measured as the number of patients failing first SBT or first extubation attempt and requiring up to 7 days to extubate (difficult weaning group/group 2); failing first SBT or first extubation attempt and requiring more than 7 days to extubate (prolonged weaning group/group 3),
- (vii) Weaning Complications, measured as the number of patients: requiring non-invasive ventilation post-extubation; ventilated more than 7 days post randomization, ventilated more than 21 days from time of intubation (prolonged MV group); receiving tracheostomy post-randomization, requiring re-intubation (up to 7d after planned extubation)
- (viii) Tolerance of modes, measured as number of patients ever requiring A/C mode post randomization; number of patient-days requiring A/C mode post randomization,
- (ix) Cumulative dose of narcotics (converted to morphine equivalents); benzodiazepines (converted to midazolam equivalents); propofol, and dexmedetomidine
- (x) Number of patients and number of patient-days receiving any antipsychotic medication
- (xi) Sensitivity analyses of primary and secondary outcomes defining “successful extubation” as “48 hours without reintubation”
- (xii) Sensitivity analyses of primary and secondary outcomes assigning a value of 0 ventilator-free days to any participant who dies at any time during the study period

The subgroups for a priori subgroup analyses are:

- (i) Duration of mechanical ventilation prior to randomization greater than 5 days
- (ii) Failed SBT vs. failed CPAP 0 trial vs. failed weaning criteria prior to randomization
- (iii) Failed extubation prior to randomization
- (iv) Mild, moderate, severe frailty

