Proportional assist ventilation with load-adjustable gain factors is a mechanical ventilation mode (PAV+ mode) that delivers assistance to breathe in proportion to the patient's effort [14, 15]. The proportional assistance, called the gain, can be adjusted by the clinician to maintain the patient's respiratory effort or workload within a reasonable range. PAV+ mode is the only ventilation mode that allows measurement and targeting of a specific range of respiratory muscle activity by the patient [16]. Currently, pressure support ventilation (PSV) mechanical ventilation mode is the most common mode used after the acute phase of illness [17] and thus may be considered the standard of care for assisted breathing of patients during the recovery phase of acute respiratory failure [18]. Several small studies have shown short term advantages of PAV+ over PSV, including improved patient-ventilator synchronization, improved adaptability to changes in patient effort, and improved sleep quality [7, 12, 19, 20, 21, 22]. One randomized controlled trial (RCT) compared PAV+ mode to PSV over 48 hours and demonstrated it was better tolerated [23], but to date, there has been no large, multi-centre RCT comparing the two modes head-to-head to evaluate impact on clinically important, patient-centred outcomes. This study is poised to answer several research questions that have remained unanswered to date: (1) Does PAV+, set to maintain a workload of breathing within the normal range, decrease duration of MV and (2) improve other clinical outcomes compared to the current standard of care using PSV? (3) Do patients randomized to PAV+ receive fewer administered sedatives and/or antipsychotic medications than patients randomized to PSV, and (4) are pain/agitation/sedation/delirium scores different between patients on PAV+ vs. PSV? (5) In addition to mode of ventilation, do factors such as age. sex, frailty score, comorbidity index, severity of illness, prior duration of MV, prior SBT/extubation failure, work of breathing, sedation, or early mobilization, influence duration of weaning and weaning success?

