4.7 Baseline patient characteristics

Baseline data will be described using mean and standard deviation, median and interquartile range, counts and percentages as appropriate. Baseline characteristics will include but will not be limited to

- Diagnosis (operative vs. non-operative)
- Subdiagnosis for non-operative subjects (respiratory, cardiovascular, other)
- Charlson comorbidity index and components
- APACHE score
- SOFA score
- Cumulative fluid balance
- Neuromuscular blockade
- Steroid use
- Antipsychotic use
- Baseline sedation category

5 Outcomes

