5.5.1 Assessment of Co-interventions

Co-interventions occurring during the study will be described as well as other patient characteristics that were collected during follow-up such as SOFA score, daily fluid balance, cumulative dose of sedating medications, number of patients and patient-days receiving any antipsychotic medication.

5.5.2 Sedating Medications and Sedation, Agitation, and Delirium Scores:

Sedating medications are routinely administered as part of routine ICU care, and may influence duration of IMV (reference). As such, they are co-interventions. However, a patient's requirement for sedating medications may be influenced by many factors, including acuity of illness, presence of delirium, pain, and patient-ventilatory dyssynchrony. Since patient-ventilator dyssynchrony may differ between PAV+ and PSV, mode of ventilation may influence amount of sedating medications administered, and amount of sedating medications administered may in turn influence duration of IMV. We will take the following approach to analyzing sedating medications and sedation, agitation, and delirium scores:

Drug conversions

- 1. Opioids daily total dose of all opioid medications will be converted to morphine IV equivalents [25, 26, 27]
- 2. Benzodiazepines daily total dose of all benzodiazepine medications, propofol and dexmedetomidine will be converted to midazolam IV equivalents [28] [26]

3. Other sedative infusions – we had planned to analyze propofol, dexmedetomidine, and ketamine separately; however, a recent study [28] described a method for converting propofol and dexmedetomidine to midazolam equivalents based on "expert opinion and clinical practice;" we will use their conversion factor to convert propofol and dexmedetomidine to midazolam equivalents and include in the total daily dose of midazolam IV equivalents. Ketamine will be analyzed independently.

Drug doses will be compared across groups using mixed effects models adjusted for baseline and with a time by treatment interaction term.

The number of patients and number of patient-days receiving any antipsychotic medication will be compared between groups.

Sedation/agitation scores

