6.4 Covariates of Interest

The following were pre-specified as covariates are of particular interest

- 1. Duration of mechanical ventilation prior to randomization in 1) days and 2) as a binary indicator for greater than 5 days or not.
- 2. 2. Failed spontaneous breathing trial (SBT) vs. failed continuous positive airway pressure (CPAP) zero trial (CPAP trial of 0 cmH2O) vs. failed weaning criteria prior to randomization
- 3. Failed extubation prior to randomization (Failed extubation vs. No extubation attempt prior to randomization)
- 4. Mild, moderate, severe frailty assessed using the Clinical Frailty Scale (CFS) [30]. There should not be anyone with CFS 9 (Terminally ill) in the study based on the inclusion criteria

- Mild: CFS 1 to 3 (very fit to managing well)
- Moderate: CFS 4 to 6 (managing well to mildly frail)
- Severe: CFS 7 to 8 (severely frail to very severely frail)

In addition to the above pre-specified covariates, we will explore the effects of baseline cumulative fluid balance and baseline sedation category in adjusted analyses. In addition, baseline use of antipsychotics, neuromuscular blockers and steroids will be described.

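### The antipsychotic patient count includes patients already on the drug at randomization and has no stated baseline adjustment, so it is less sensitive than it could be

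*Protocol*

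**What the plan says.** Protocol 6.3(x) defines the outcome as "Number of patients and number of patient-days receiving any antipsychotic medication". It does not limit the outcome to patients free of the drug at randomization.

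SAP 5.5.2 gives the whole analysis in one sentence: "The number of patients and number of patient-days receiving any antipsychotic medication will be compared between groups". It names no test, effect measure or covariate, and SAP 6.2 adds none. In the same section the other medications are treated differently: "Drug doses will be compared across groups using mixed effects models adjusted for baseline and with a time by treatment interaction term".

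Baseline use is to be available: SAP 4.7 lists "Antipsychotic use" among the baseline characteristics. SAP 6.4 puts baseline fluid balance and sedation category into adjusted analyses, but for antipsychotics says only that "baseline use of antipsychotics, neuromuscular blockers and steroids will be described".

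The outcome serves a stated question, number (3) in SAP 1.1: "Do patients randomized to PAV+ receive fewer administered sedatives and/or antipsychotic medications than patients randomized to PSV".

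**The concern.** A patient who arrives on an antipsychotic and simply continues counts as an event in either arm. Such patients carry little information about ventilation mode, but they enter both numerators and add variance to the comparison. The crude odds ratio moves toward 1, and a real reduction in new prescribing is harder to see. Baseline use should predict later use strongly, and the SAP already accepts the principle of baseline adjustment for sedatives and opioids. At stake is whether a null result here could be read as a fair answer to question (3).

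**Working it through.** **The plan's own figures.** Neither document gives a rate, effect size or power for this outcome. The sample size rests on the primary outcome alone. At a hazard ratio of 1.30, two-sided 5% and 80% power, the Schoenfeld formula 4(1.960 + 0.842)²/(ln 1.30)² gives about 456 events, as stated. Then 529/0.95 = 556.8, so 557, or 558 for equal arms. The 279 per arm used below is therefore the plan's figure; every rate below is an assumption.

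**Notation.** b is the share on an antipsychotic at randomization, c the share of those who receive one afterwards, p the share of non-users who start, and n = 279.

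**Unadjusted count.** The rate in each arm is q = bc + (1 − b)p. If c is equal in both arms, the difference is (1 − b)(p₁ − p₂). Power is Φ[(|q₁ − q₂| − 1.96·SE₀)/SE₁], with the usual pooled (SE₀) and unpooled (SE₁) two-proportion standard errors.

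**Stratified count.** The stratum differences are weighted by b and 1 − b. The variance is [b·V_users + (1 − b)·V_non-users]/n, where V is the sum over the two arms of rate × (1 − rate), with the pooled rate for SE₀.

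**One case in full: b = 20%, c = 95% in both arms, p = 20% against 12%.**
- PSV: 0.2 × 0.95 + 0.8 × 0.20 = 0.350. PAV+: 0.2 × 0.95 + 0.8 × 0.12 = 0.286. The difference is 0.064.
- Crude odds ratio: (0.286/0.714)/(0.350/0.650) = 0.74. Among non-users it is (0.12/0.88)/(0.20/0.80) = 0.55.
- Unadjusted: SE₀ = 0.0394, SE₁ = 0.0393. Power = Φ[(0.064 − 0.0773)/0.0393] = 0.37.
- Stratified: SE₀ = 0.0290, SE₁ = √[(0.2 × 0.095 + 0.8 × 0.2656)/279] = 0.0288. Power = Φ[(0.064 − 0.0568)/0.0288] = 0.60, or 0.61 by simulation.

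The weighted difference is 0.064 both ways. Stratification gains by removing the variance between baseline users and non-users.

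**Same rates across baseline use:**

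| Baseline use | Crude OR | Unadjusted power | Stratified power |
|---|---|---|---|
| 5% | 0.62 | 0.61 | 0.71 |
| 10% | 0.67 | 0.51 | 0.67 |
| 20% | 0.74 | 0.37 | 0.61 |
| 30% | 0.79 | 0.27 | 0.52 |

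With no baseline users, power would be about 0.73. Part of the fall therefore cannot be recovered: stratified power drops too, because fewer patients can start the drug.

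**Less favourable inputs, unadjusted against stratified power:**

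| Baseline use | Continuation 70% vs 60%, starts 20% vs 12% | Continuation 95% both, starts 50% vs 40% |
|---|---|---|
| 10% | 0.66 vs 0.72 | 0.57 vs 0.61 |
| 20% | 0.62 vs 0.72 | 0.48 vs 0.55 |
| 30% | 0.60 vs 0.71 | 0.39 vs 0.48 |

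The gaps are about 6, 10 and 12 points in the first case and 4, 7 and 9 in the second. At 5% baseline use both are roughly 3 points.

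**Patient-days.** No standard deviation is given, so the effect on this measure was not quantified.

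**The case against.** The strongest reply is that there is no planned power to lose. The outcome was never powered, SAP 5.2 (item 9) lists these drugs as monitored co-interventions, and SAP 3.1 rejects reading results against a 5% threshold and promises an estimate, confidence interval and p-value for every outcome. That stands, and it limits the weight of the point. It does not remove it: SAP 5.5.2 still commits to a between-group comparison, and a larger standard error also means a less precise treatment effect.

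Four stronger readings are tempting, and the documents do not support them.
- *The comparison is biased.* It is not. Randomization balances baseline use on average.
- *The test loses much of its power, without qualification.* That needs baseline, continuation and new-start rates, and the documents give none. The loss to the method is the gap between the two analyses, not the whole fall from 0.73.
- *Any use is the wrong outcome.* Question (3) asks about the amount received, and total use answers it. A crude odds ratio nearer 1 is the true effect on total use. New starts are a different question.
- *Patient-days are diluted in the same way.* They can register earlier stopping among baseline users, so the automatic-event argument does not carry over.

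It is also fair to say that an unadjusted test is inferred from silence. The SAP names no method, so the remedy is partly one of completing the specification.

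**Conclusion.** The point holds as an avoidable loss of sensitivity in a secondary patient count. Baseline users are included, baseline use is only described, and this is out of step with the baseline adjustment of sedative and opioid doses. Under the main assumptions (95% continuation in both arms, starts of 20% against 12%, 279 per arm), stratification gains about 10 points of power at 5% baseline use, 16 at 10%, and 24 to 25 at 20% to 30%. Under the less favourable inputs the gain is about 3 to 12 points. Stratification gained power in every case examined with baseline users present, but the documents do not fix how much. For patient-days the expected benefit is mainly lower between-patient variance, of unknown size.

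**What to change.** In SAP 5.5.2, state that the number of patients receiving an antipsychotic will be compared by logistic regression, or a Mantel-Haenszel analysis, adjusted for antipsychotic use at randomization, with an odds ratio and 95% confidence interval. Show the crude counts by arm beside it, since the adjusted odds ratio is conditional on baseline use and will tend to lie further from 1 than the crude one. Include the same baseline indicator when comparing patient-days. Keep total use as the outcome, and add new starts among patients not on an antipsychotic at randomization as a supplementary result.

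The cost is a few lines of SAP text and one covariate already listed in SAP 4.7. No new data or patients are needed. The change should be made before any analysis by arm.
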